The *primary exploratory outcome* of interest is depressive symptoms (measured by BDI-II); the *secondary outcome* is peer violence (CTS-2). Under [name] guidance, we will first calculate preliminary estimates of the between-groups differences in depressive symptoms (continuous) and peer violence (counts), with 95% confidence intervals, at 8- and 16-week follow-up assessments, adjusted for baseline values. An intent-to-treat approach (all patients randomized to intervention will be retained in analysis) will be used to address potential problems inherent in following only treatment completers and the potential for differential attrition across conditions.[140, 141] In cases of loss-to-follow-up, baseline observations will be carried forward.

Generalized linear mixed models (GLMM)[142, 143] that employ likelihood-based estimation approaches will then be used to evaluate changes in depressive symptoms and number of fight episodes at the 8-week and 16-week follow-ups. Intervention condition will be considered the primary predictor variable. Race and gender will be included as secondary predictors. We will control for baseline levels of the outcome variable (e.g. severity of baseline depressive symptoms and peer violence) as well as the linear and quadratic effects of time. We will also examine potential moderators of the intervention effect, including gender, race, and baseline coping skills. In GLMM, no missing data imputation will be employed, as the models produce consistent estimates in the presence of data missing-at-random.[144, 145] **Analyses will serve as a training activity.**

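### The mixed model has no condition-by-visit term, so it gives one effect pooled over weeks 8 and 16, and the only visit-specific estimates carry baseline forward

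*Combined protocol and SAP*

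**What the plan says.** Under Exploratory hypothesis testing (Statistical Analysis, Phase Two, Aim 3) the plan has two steps.

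- **Preliminary step.** Between-group differences in depressive symptoms and peer violence are estimated "with 95% confidence intervals, at 8- and 16-week follow-up assessments, adjusted for baseline values". For missing data: "In cases of loss-to-follow-up, baseline observations will be carried forward". The intent-to-treat rationale mentions "the potential for differential attrition across conditions".
- **Mixed model.** Likelihood-based GLMMs are then "used to evaluate changes in depressive symptoms and number of fight episodes at the 8-week and 16-week follow-ups". On the predictors: "Intervention condition will be considered the primary predictor variable". Race and gender are secondary predictors. On baseline: "We will control for baseline levels of the outcome variable", and in the same sentence "as well as the linear and quadratic effects of time". On missing data: "In GLMM, no missing data imputation will be employed", because the models are consistent under missing at random.

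The effect modifiers named are gender, race and baseline coping skills. Neither time nor visit is among them.

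Aim 3b looks for a fall in depressive symptoms at both 8 and 16 weeks. The texts run for eight weeks, so week 8 is the end of the intervention and week 16 shows whether any effect lasts.

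**The concern.** A condition main effect without a condition-by-visit term imposes one treatment effect on both visits. An effect present only while texts are being sent, one that is constant, and one that appears only afterwards can all give the same coefficient. Those patterns have different implications for a later trial, and the Sample size paragraph makes an observed between-group effect part of the case for one.

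The estimates that do separate the visits are the preliminary ones, and these treat every lost participant as unchanged from baseline. So the method chosen for its behaviour under missing at random does not answer the visit-specific question, and the method that answers it relies on carry-forward.

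A secondary oddity is that two follow-up visits support only one time contrast, so linear and quadratic time cannot both be fitted if time is coded as nominal visit.

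**Working it through.** The plan states no figure that this point turns on, so there is none to reproduce first.

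**Inputs from the documents.** Outcome visits at weeks 8 and 16; 120 randomised; 20% lost by week 16, leaving 96; SD 4.5 and difference 2 (Sample size paragraph). The last two are PHQ-9 values, and no BDI-II SD is given.

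**Assumed inputs.** Week-8 loss 10%; control improvement 3 points; correlation rho between any two occasions 0.3, 0.5 or 0.7; loss monotone.

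**1. What the model can estimate.** At t = 8 and 16, t² = 24t - 128 exactly (24×8 - 128 = 64; 24×16 - 128 = 256). The design [1, condition, baseline, t, t²] has rank 4 of 5. Replacing t² with condition-by-visit gives rank 5 of 5.

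**2. Pooling.** Random-intercept models were fitted to one simulated set of 4,000 participants, using the same random numbers for three true patterns:

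| True effect, week 8 / week 16 | Main effect only | With condition-by-visit, week 8 / week 16 |
|---|---|---|
| -4 / 0 | -1.86 | -3.81 / 0.10 |
| -2 / -2 | -1.86 | -1.81 / -1.90 |
| 0 / -4 | -1.86 | 0.19 / -3.90 |

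The gap between -1.86 and -2 is chance in that data set. What matters is that the three main-effect results are identical.

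**3. Weight on each visit.** After baseline adjustment the residual correlation is r = rho/(1 + rho), which is 1/3 at rho = 0.5. With 80% seen at both visits and 10% at week 8 only, the information row sums are 0.8/(1 + r) + 0.1 = 0.7 for week 8 and 0.8/(1 + r) = 0.6 for week 16. Week 8 therefore has weight 0.7/1.3 = 54%. A true -2 then 0 pools to about 0.54 × (-2) = -1.1; a true 0 then -2 pools to about 0.46 × (-2) = -0.9. A constant -2 is estimated without bias.

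**4. Carry-forward, loss unrelated to outcome.** The expected difference is (1 - p_int) × change_int - (1 - p_ctl) × change_ctl, with changes of -5 and -3.

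| Loss, intervention / control | Expected difference (true -2) |
|---|---|
| 10% / 10% | 0.9×(-5) - 0.9×(-3) = -1.8 |
| 20% / 20% | 0.8×(-5) - 0.8×(-3) = -1.6 |
| 10% / 30% | 0.9×(-5) - 0.7×(-3) = -2.4 |
| 25% / 15% | 0.75×(-5) - 0.85×(-3) = -1.2 |

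With equal loss the control improvement cancels. With unequal loss it does not: for control improvements of 0, 1.5 and 5 points, 10%/30% gives -1.8, -2.1 and -2.8, and 25%/15% gives -1.5, -1.35 and -1.0.

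**5. Carry-forward, loss depending on the week-8 score.** Take 20% loss per arm after week 8, by a logistic model with slope 1 per SD and opposite signs in the two arms. With a common correlation the result stays near -1.6. With correlation 0.4 between baseline and each visit and 0.7 between visits, it is about -2.0 or -1.2, depending on which arm has which sign. With 0.3 and 0.7 it is about -2.1 or -1.1. In simulated week-16 loss driven by the week-8 score, with a common correlation, the condition-by-visit model gave -1.98 to -2.02.

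**6. Cost in precision.** At rho = 0.5 the visit information matrix per randomised participant is [[1.0, -0.3], [-0.3, 0.9]], with determinant 0.81. Relative variances are 0.9/0.81 = 1.111 at week 8, 1.0/0.81 = 1.235 at week 16 and 1/1.3 = 0.769 pooled. Interval-width ratios to the pooled interval are √(1.111/0.769) = 1.20 and √(1.235/0.769) = 1.27. For rho of 0.3 and 0.7 they are 1.25 and 1.17 at week 8, and 1.32 and 1.23 at week 16.

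**7. Testing the difference between visits.** With 48 per arm, SE = √(2 × 4.5² × (1 - rho) × 2/48), which is 0.92 at rho = 0.5. Power is 59% for a full 2-point fade (45-80% over rho 0.3 to 0.7) and 19% for a 1-point fade (15-29%).

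**The case against.** **The interaction is unstated, not excluded.** The GLMM sentence speaks of changes at both follow-ups, which may show intent. This stands, and a reader should not infer that the sponsor has ruled visit-specific effects out. But no listed term delivers them, and the list of modifiers omits visit.

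**Visit-specific differences are already planned, and pooling suits a small pilot.** Also fair: Aim 3b does not go unanswered, and pooling is more precise. What remains is that the answer by visit comes only from carry-forward.

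**The quadratic term might be estimable.** If time is coded from actual assessment dates, the design reaches full rank, though curvature then rests only on scatter in visit timing. The reference cited for GLMM is a growth-curve methods paper, and BDI-II is also collected at baseline (Table 11.3), so a three-occasion growth model is conceivable. The quadratic would then be estimable, but baseline is listed as a covariate, and condition-by-time terms would still be needed. With baseline added as an outcome and no such terms, the fits in the table of step 2 gave -1.24 for all three patterns. A reader might infer that the quadratic term invalidates the model. It does not: software would drop the redundant column and leave the condition effect unbiased.

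**The largest distortions rest on assumptions.** The documents give no loss by arm and no control improvement, and mention differential attrition only as a possibility. The -2.4 and -1.2 figures show direction, not a forecast. A reader might also infer that equal loss always pulls carry-forward estimates towards zero. Step 5 shows that this is not general.

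**Conclusion.** The point holds, and it is minor. As written, the analysis that is valid under missing at random gives one effect averaged over weeks 8 and 16, with about 54% of the weight on week 8 under the assumed loss. It cannot separate a fading effect from a lasting or late one. That conclusion follows from the listed terms and needs none of the assumed numbers.

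The size of the harm does need them. On PHQ-9 inputs, with 20% loss per arm unrelated to outcome, the planned week-16 estimate would be about -1.6 for a true -2. With unequal loss, or loss that depends on earlier scores differently by arm, it could be too small or too large.

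The redundant quadratic term is a drafting matter that depends on nominal visit coding. A reader might infer that the trial's main conclusions are at risk. The documents do not support that: acceptability, feasibility and fidelity are the primary outcomes and are untouched, and the efficacy analysis is described as exploratory and not powered.

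**What to change.** Replace linear and quadratic time with a two-level visit factor and add condition-by-visit. Suggested wording:

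*Responses are the week-8 and week-16 scores. Fixed effects are condition, visit, condition-by-visit, the baseline value of the outcome, gender and race, with a random participant intercept. The week-8 and week-16 between-group contrasts from this model, with 95% confidence intervals, and their equally weighted average are the governing estimates. Estimates with baseline carried forward are a sensitivity analysis. Moderator analyses use the visit-averaged effect.*

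Use the same structure with a log link for fight counts.

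This takes one paragraph and no new data. The price is precision: visit-specific intervals are about 17-25% wider at week 8 and 23-32% wider at week 16 than the pooled interval (assumed 10%/20% loss, correlation 0.7 to 0.3). Power to test a change between visits is limited, so report that difference as an estimate only.

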14. PROTECTION OF HUMAN SUBJECTS

Summary: For this clinical study, all data collection sheets and computerized databases will use a unique numeric code to identify specific subjects. The code sheet will be kept in a locked file cabinet in [name] locked office, and on password protected files on secure hard drives owned by [name] institution. We intend to seek approval for this study from the human protection committees at Rhode Island Hospital; no study activities will be initiated without full institutional review board approval. All members of the research team have already completed training and received certification in Human Subjects Research Protection (CITI Program) and HIPAA regulations. They will continue to renew this training in compliance with Rhode Island Hospital and Brown University policies. Additionally, **a Certificate of Confidentiality will be obtained** for this study from NIH once IRB approval has been granted.

14a. Risks to the Subjects

14a.1. *Human Subjects Involvement and Characteristics:*

In Specific Aim 2, approximately 16 adolescents will participate in a series of open trials of the ED-based preventive intervention. In Specific Aim 3, the novel "ED+text" intervention will be studied in a randomized controlled pilot trial, with 50 participants in the "ED+text" arm and 50 participants in the enhanced usual care (EUC) arm. The ethnic and racial composition of the study group will be expected to represent that of the pediatric population seen in the Rhode Island Hospital ED, identified to be approximately 40% Hispanic and 25% black or African American by my own pilot study (data analysis in progress). Children aged 13 to 17 will be included in the study.

Inclusion Criteria. To recap what was described in Section 11c above: *Inclusion criteria for screening include:* being medically stable; mentally and physically able to assent; English-speaking; and having a parent present to consent. *Exclusion criteria for screening include* a chief complaint of sexual assault or child abuse; a chief complaint of acute suicidality or psychosis; or being in police custody. *Additional inclusion criteria for enrollment (in Aim 2 or Aim 3) include* a PHQ-9 score ≥ 5 and past-year peer violence (according to CTS2).

Potentially eligible participants will be **excluded** from enrollment if they or their parents do not consent to audio-taping of the in-ED session or if they meet criteria for severe depression (PHQ-9 > 20). Additionally, patients who are deemed (based on in-ED assessment by a clinician, after notification about a positive screen for suicidality) to need a psychiatric hospitalization will be ineligible.

Participants in Aim 1 may be eligible for Aim 2, but will be restricted to less than 1/3 of the Aim 2 sample. Participants will be ineligible for Aim 3 if they have participated in Aims 1 or 2.

Rationale for including special classes of subjects. This research will involve children between the ages of 13 and 17 inclusive. The age range is dictated by the prior research showing elevated risk for depression and peer violence among teens in this age range. It is of utmost importance to study this "vulnerable population" because they are an understudied population; a population at high risk of negative outcomes; a population with limited access to and use of traditional mental health services; and a population with high possible benefits if effective, accessible preventive services can be developed.

All ethnicities and races will be equitably included. Only English-speaking patients will be eligible for two reasons. First, our previous and ongoing studies show that the vast majority of Hispanic adolescents speak fluent English.[9, 149, 150] Second, due to budgetary constraints inherent in this training grant, it would be difficult to fund a bilingual interventionist and translation of all materials into Spanish.

14a.2. *Sources of Materials:*

Materials will be collected from adolescent participants in the study. Data will be collected from participants primarily using a tablet laptop computer and audio-taped interviews; some de-identified data may be collected through secure text messaging services in Aims 2 and 3. Minimal data will be collected from Medhost and Lifelinks regarding participants' ED utilization and hospital admissions after initiation of the study. Data that are obtained specifically for research purposes will be collected only with written assent from youth and written consent from a parent or guardian. Minimal clinical data will be collected on patients that refuse to participate in the study, on patients that the research assistants fail to approach about the study, and on patients that are excluded from the study. This data will be obtained from de-identified emergency department medical records, to assess characteristics of patients not approached or who refuse participation.

Linkages to subjects and access to subject identities. For each stage of the research, participant names and contact information will be maintained in a secure, password-protected recruitment/enrollment database. Once individuals enroll in the study, names will be linked to participant ID number *only* in this database, which will be kept in a restricted access folder on a secure server. This file will be assigned a code name unrelated

to the name of the study. Baseline, follow-up, and focus group data will be coded according to participant ID number, and will contain no protected health information.

To facilitate scheduling the 8 week follow-up interview during Aim 2 only, participants *may* choose to participate in the YouCanBookMe Limited scheduling service. This is a voluntary third party, encrypted service that schedules appointments using the participant's email address, first initial, and last initial. The data will only be scanned by the system for the purposes of scheduling and rescheduling the participant's follow-up interview. Once the scheduled interview is complete, members of the research team will erase the participant's email from the YouCanBookMe encrypted server. While this information will be kept in confidence by the research team, and while YouCanBookMe assures that it will not access the information for any promotional purpose, we cannot prevent outside forced entrance into the YouCanBookMe server.

Signed consent and assent forms will be kept in a double-locked file cabinet in the PI's locked office, separate from any other project data. Once data collection for each stage of the study is completed, the corresponding recruitment/enrollment database will be deleted as it is unnecessary to maintain the link between participant identity and study data. All information collected as part of this study will be accessible only to research staff that has completed mandatory training in the protection of human subjects.

Data collection. Data will be collected solely for the purposes of this research project. All information collected as part of this study will be obtained only by research staff employed by the project. Data sources include: 1) participants' responses to baseline and follow-up questionnaires, 2) confidential audio-taped semi-structured interviews, and 3) participants' responses to text-messages. In Aim 2, data will be collected at screening, baseline and after the intervention. In Aim 3, data will be collected at screening, baseline, 8 weeks post-enrollment, and 16 weeks post-enrollment.

14a.3. *Potential Risks:*

Every effort will be made to ensure that study participants are protected from risks. The risks are as follows: 1) potential coercion, 2) loss of confidentiality, 3) emotional discomfort during the assessment and/or program sessions, and 4) further violence if an assailant is made aware of program involvement. The protection against each risk is described in detail in **Section 14b.2, below**.

14b. Adequacy of Protection Against Risks

14b.1. *Recruitment and Informed Consent:*

Screening and Consent. A research assistant (RA) will be present in Hasbro Children's ED on randomly selected shifts (selection weighted according to patient volume). All patients between ages 13 and 17 will be pre-screened by the RA. If the patient is triaged as stable, and is not presenting for with a chief complaint of suicidality, psychosis, sexual assault, or child abuse, the RA will approach the patient and his/her family once the patient is put in a private treatment room. After reading a script to the parent and child, verbal consent/assent will be obtained from the parent/legal guardian and the child. Then, youth will complete a computerized screening survey. The adolescent and his/her parent will be informed that the adolescent's answers to study questions may be used to determine their eligibility for a research program. After completion of assent/consent, the teen will then be administered the screening questionnaire, including PHQ-9, and CTS-2. Additionally, to reflect my experience with 2 different screening processes during my pilot grant, we will administer additional questions drawn from Add Health, YRBS, and other relevant materials about other behaviors (which I and my mentors have found increases participant honesty on all questions; in studies where we only administer the screening questions of interest, rates of self-report have decreased significantly). All participants will be able to choose a small gift (worth \$1-2) as compensation for their time.

If an adolescent screens positive for mild-to-moderate depressive symptoms (PHQ-9 between 5 and 20) and past-year peer violence, s/he will be informed that they are eligible for the research program. Adolescents and their parents will be informed that their responses to screening questionnaire indicate that they are eligible for a program to help build mental health and prevent fights. Screened participants who agree to be part of the study will complete an additional *written* assent/consent form for Aims 2 and 3.

All individuals who agree to participate in the screening will be given referral information for a variety of community resources including community mental health services and violence prevention organizations.

During recruitment, research staff will inform the subject of the general nature of the study, their privacy rights, expectations for their participation, the voluntary nature of their participation, and that their participation can be withdrawn at any time. Participants will be assured that refusal to participate will not affect their care in any way. At all times, research staff will make explicit the voluntary nature of the subjects' participation as well as potential situations for breaking confidentiality. Recruitment procedures will be HIPAA compliant and have been IRB approved in past studies.

Referrals. All participants in the screening will receive a handout of mental health and violence prevention resources. If an adolescent screens positive for severe depressive symptoms at any time during the study, regardless of eligibility for the study, the RA will discuss the score with the family, notify the attending pediatric emergency physician, and offer to contact the adolescent's pediatrician.

If an adolescent discloses suicidality or if the patient's family so desires, the RA will alert the patient's clinician (if appropriate) who will immediately initiate a psychiatric evaluation in the ED, or will contact the patient and his/her parent if disclosure occurs outside of the ED. (See "Mandatory Reporting & Crisis Management," below). If a patient is deemed to need psychiatric hospitalization based on the screening, they will be withdrawn from the study.

Assessments and Remuneration. In **Aim 2**, participants will complete a baseline assessment, an 8-week follow-up assessment and interview; in **Aim 3**, participants will complete a baseline assessment, an 8-week interview and an 8-week and 16-week computerized follow-up assessment. Follow-up assessments will take place online, on the telephone, or in private rooms at the PI's departmental office (separate from the ED) where privacy and confidentiality can be maintained (i.e., making sure no one can overhear the conversation).

Participants will be remunerated with a gift worth ~\$1-2 for the screening survey. In **Aim 2**, participants will be compensated \$25 after completing the baseline assessment and in-ED intervention, \$10/month for text-messaging plans, an additional \$5 incentive if they complete the 8-week follow-up survey *prior* to the 8-week follow-up interview, and \$50 for completing the 8-week follow-up. In **Aim 3**, participants will be remunerated \$25 after completing the baseline assessment and in-ED intervention, \$40 for completing the 8-week follow-up, \$50 for 16-week follow-up, and \$10/month for text-messaging plans. Participants will also receive \$5.00 for notifying us of any address/telephone changes, and an additional \$5 for completing the 8-week and 16-week surveys *prior* to their due date.

14b.2. *Protection Against Risk*

Risk 1): Potential Coercion.

The risk of potential coercion will be minimized by following standard procedures for obtaining the informed consent from parents and assent from teens. Study personnel will fully explain the study procedures, risks, benefits, and alternatives to teens and their parents. Participants and their parents will also be reminded that study participation is voluntary and that refusing to participate or withdrawing from the study at any time will not result in any negative consequences on their care.

Risk 2): Confidentiality

Potential risk will be minimized by strictly adhering to the guidelines for research outlined by the Lifespan IRB, Rhode Island state law, the Federal Health Insurance Portability and Accountability Act of 1996 and its regulations ("HIPAA"), and the DHHS Federal Policy for the Protection of Human Subjects (45 CFR Part 46 Subpart D). In particular, the risk of loss of confidentiality will be minimized by the following specific procedures:

UNIVERSAL:

- (a) All research staff will sign a pledge of confidentiality and will understand that violation of confidentiality is reason for dismissal. Training of staff includes information about the importance of confidentiality and techniques to maintain confidentiality of all information reported by research participants.
- (b) Any collected information will be referenced only by participant ID #.
- (c) The only list connecting the participant ID # to the participants' names will be kept in a password-protected folder on the PI's password-protected computer (which is owned by the hospital, and which is on the hospital's HIPAA-secured research server). This list will be deleted as soon as each phase of the study is completed.
- (d) The consent forms and research materials will be kept in separate double-locked cabinets in the PI's locked office.
- (e) All computerized information will be maintained on password protected, HIPAA-compliant computers owned by the PI's hospital which use only HIPAA-compliant research server.
- (f) All computerized surveys will be completed using REDCAP.
- (g) No names, only identification codes, will be used in presenting data in lectures, seminars, and papers.

SEMI-STRUCTURED INTERVIEWS:

- (a) Semi-structured interviews will take place in a private room at the site of the participant's choosing (e.g. ED, PI's departmental office, library, telephone) where confidentiality can be assured

- (b) Ground rules will be set at the beginning of the interviews, instructing participants to not identify themselves or others by name, and emphasizing the confidentiality of everything discussed [with the exception of suicidality/homicidality/child abuse].
- (c) Participants will be not be referred to by name on the audiotapes.
- (d) Prior to transcription, the digital tapes will be kept in a password protected format on a password-protected Lifespan hard-drive accessible only to the PI and the RA. The recordings will be maintained for 5 years in compliance with human subjects policies.
- (f) Transcripts will be reviewed only by the PI and her research team.

TEXT-MESSAGING:

- (a) All text-messages will be sent using a secure text messaging system (hosted by Reify Health, a company that we have worked with in the past for similar projects) that will not store data remotely; the text-message server is located behind a research-compliant firewall.
- (b) Text-message data will be maintained in a password-protected, restricted-access hard drive in the Department of Emergency Medicine.
- (c) Text-message data will be monitored exclusively by the PI and her research team.

Participant confidentiality will be breached only to protect the safety and welfare of research participants and only in accordance with state and federal law. The exceptions to confidentiality include if the adolescent reports suicidality, homicidal thoughts, or that he/she is the victim of child abuse or neglect. If the adolescent reports suicidality or homicidality, parents will be notified, and an emergency psychiatric evaluation for inpatient hospitalization will be facilitated with the Pediatric Emergency Psychiatric Service at Rhode Island Hospital. If necessary, authorities will be notified. If child abuse or neglect is reported, a report will immediately be filed with the Department of Children, Youth and Families. This exception to breaking confidentiality – the case where a participant reveals child abuse, suicidality, or homicidality – will be explained in detail to both participants and parents prior to completing the assent/consent.

Finally, information collected in this research study will not be available to clinicians, parents, or to other researchers. All data will be collected specifically for use on this project.

Risk 3) Emotional Discomfort

Of note, members of the proposed mentorship team have substantial prior clinical and research experience with high-risk populations as evidenced through their biographical sketches. [name] has extensive clinical and research experience developing interventions for depressed, suicidal, and alcohol-abusing adolescents. [name] has extensive clinical and research experience with adolescent violence and substance abuse prevention.

Parental distress: If parents report feelings of distress as a result of being notified that their child is eligible for this research project, clinical resources will be offered. These include referrals for mental health counseling and information about violence hotlines and local community organizations.

Assessments: The assessment instruments are commonly used in research and clinical practice. We will minimize distress by presenting questions/program techniques in a supportive manner, assuring participants that they may refuse to answer questions that make them uncomfortable, and reminding them that they may terminate the assessment and/or intervention at any time.

Although there is extremely low risk of an adverse reaction to the screening survey or qualitative interviews (and, in fact, benefits to participation in similar research have been demonstrated),[151] all potential participants will be provided with a list of community resources at the same time that they are approached by the RA about participation in the study. To minimize negative consequences from the screening survey or semi-structured interviews, the RA will be trained to immediately terminate the assessment and alert the PI and the patient's clinician in the case that the subject demonstrates physical or psychological instability.

Additionally, on completion of baseline and follow-up assessments, the RA will be alerted by the computer if a participant has reported suicidality or severe depressive symptoms. The RA will contact [name] or [name] at that time, and the teen will be further evaluated for risk of harm to self or others. To the extent that the adolescent is determined to be a risk to himself/herself or others, the parent will be notified and a referral to an emergency evaluation with the Pediatric Emergency Psychiatric Service at Rhode Island Hospital will be made.

Regarding the text-messaging component of the study, text message assessments do NOT induce depression despite repeated assessments of negative mood.[152] Momentary assessments have also been shown to be acceptable, feasible, and appropriate when used to ask sensitive assessments (e.g., suicidality,

mood, alcohol and substance use, eating disorders, and violence) among a variety of populations, including school-age adolescents, schizophrenics, the homeless, drug addicts, recently hospitalized suicidal patients, and college students.[153-163]

Text-message Data: Participants and parents will be explicitly instructed during the consent process that no one will be monitoring text-message data in real time. In the case of a crisis situation, the adolescent should call the provided crisis hotline number or the PI's phone number rather than text the program. Nonetheless, some participants may misinterpret these guidelines. Hence, text-message data will be reviewed regularly by the PI and her mentorship team. The software will also be designed to send participants a message that directs them to a crisis phone number, if data that is not expected by the text-message algorithm is received.

OF NOTE: This protocol mirrors that used by other text-message-based interventions for mental health and other potentially sensitive behaviors/disorders (e.g. [39, 104, 164-168]), including one that is currently ongoing with [name] and [name] at Brown University (for suicidal adolescents). Moreover, as the text messages include *no* PHI and *no* sensitive information regarding diagnoses, they easily meet or exceed HIPAA regulatory standards [169].

Ongoing Safeguards: Due to the association between violence and mental health sequelae, it is possible that some participants will experience psychiatric symptoms during the course of the program that may warrant mental health care. In order to minimize the risk of mental health deterioration, all subjects may receive mental health treatment at any time during the study. Clinical need will determine whether it is appropriate for the participant to continue in the study.

The PI's email and phone number, and a crisis hotline number, will be provided to every participant. The participant will be instructed to call the PI in case of any problems with the study, or if s/he has an immediate mental health crisis. S/he will be encouraged to call the crisis number, or 911, as well, if in need of immediate mental health services. The participant will also be provided with a wallet card explaining why she is responding to text messages, in case s/he is asked by a teacher or employer.

If a participant is identified as needing mental health treatment, the PI or her mentors will contact the participant individually for further assessment, and will notify the participants' parents of any clinical needs. Evaluation by the Pediatric Emergency Psychiatric Service at Rhode Island Hospital will be initiated on the PI's discretion at any sign of suicidality, homicidality, or child abuse. Suicidal or homicidal attempts or completions, and hospitalizations, will be monitored as serious adverse events, and will be reported our hospital's IRB according to our Data Safety & Monitoring Plan. If a patient is deemed to need psychiatric hospitalization based on the screening, they will be withdrawn from the study.

That said, we will be clear during the assent/consent process with the parents and child that we will not be conducting ongoing, real-time monitoring of the text messaging. We will emphasize that if a child needs immediate assistance, s/he or his/her parents should call 911, the child's doctor, or call one of the crisis numbers provided.

By notifying parents/guardians of the teen's risk, providing parents with the information they need to monitor their child's risk, and by conducting ongoing monitoring of the safety of the teens, **we are maintaining the highest ethical standard for our participants.**

Risk 4) Violence

The emergence of increased aggression is important and needs to be monitored. If a subject discloses increasing frequency of involvement in violence, severe physical injury, homicidality, or high risk of retaliatory violence she will be contacted by the PI for further evaluation. Although no questions will be specifically asked about child abuse or sexual assault during the study, the staff will be trained to assess and respond to participants for whom these issues arise.

Risk 5) Mandatory Reporting and Crisis Management:

As described above and in the Data Safety & Monitoring Plan, below, all instances of potential mental health or violence risks, staff will follow a written protocol regarding reporting these incidents to [name] or [name] based on call schedule, and will take appropriate referral or legal action as indicated. In addition, the IRB board at Rhode Island Hospital will be informed of any incidents. Drs. [name] and [name] will be responsible for providing training to all research staff who are conducting assessments with participants regarding procedures for identifying, managing, and responding appropriately to acute warning signs of distress that could occur as a result of the survey. Such strategies include maintaining an empathic response, acknowledging the distress through reflection, and eliciting or encouraging use of relaxation and cognitive

calming strategies. Staff will receive training in crisis assessment and management procedures in the event that participants reveal suicidal and/or homicidal ideation, child physical/sexual abuse, or concerns about safety. Drs. [name] (M.D., Emergency Medicine) and [name] (Ph.D., Clinical Psychology) will be responsible for providing regular supervision to research staff who have direct contact with patients including crisis procedures for suicide and homicide risk and clinical assessment and referral procedures for participants who are a danger to themselves or others. Supervision will focus on procedures for managing issues that could arise given the patient population, including potential crisis situations and/or adverse events.

Our crisis management procedures mirror those used by the Rhode Island Hospital Department of Psychiatry and Emergency Medicine clinical services. [name] has successfully used these safety protocols in studies at the proposed study site.

It is possible that situations will arise in which researchers are provided with information by children or families which they are legally and ethically obligated to disclose (e.g., suicidal or homicidal intent, harsh disciplinary practices, sexual abuse). All participants are informed in advance through the process of informed consent of the legal and ethical obligations of study staff should these issues arise. The consent and assent forms will clearly describe times when confidentiality must be broken, i.e., suicidality, homicidal thoughts, and a report of child physical or sexual abuse. Participant confidentiality will be breached only to protect the safety and welfare of research participants and only in accordance with state and federal law.

